## 1 Summary

Title	A PROSPECTIVE, RANDOMIZED, MULTICENTER STUDY COMPARING SEMS PLACEMENT WITH AND WITHOUT BILIARY SPHINCTERECTOMY IN PATIENTS WITH MALIGNANT BILIARY OBSTRUCTION
Study coordinator: [name] Protocol identifying number	ES vs noES-1
Protocol version date	Version 3 (06.07.15)
Background and rationale	
Placement of biliary self expanding metal stent (SEMS) is indicated when malignant common bile duct obstruction is encountered [1].
 
Currently, there is still controversy regarding the use of endoscopic sphincterotomy (EST) before the placement of biliary stents. EST may facilitate insertion of self expandable metal stent (SEMS) and also help avert the development of pancreatitis from stent-related occlusion of the pancreatic duct. On the other hand, ES is also independently associated with pancreatitis, bleeding, and perforation. [2-5].
 
Latest European guidelines indicate that EST is not necessary for inserting single plastic or metal biliary stents [1], nevertheless a more recent meta analysis showed that ES may decrease the rate of PEP [5].

Population and patient selection criteria	All the patient referred for endoscopic retrograde cholangiopancreatography (ERCP) due to malignant bile duct obstruction.
Study design and study duration	Prospective randomized, multicenter study. 18 months.
Description of study treatment/product/intervention	
All the patients will be randomly assigned to undergo ERCP with (Group A) or without (Group B) ES before biliary SEMS placement.
 
All the endoscopic procedures will be performed by experienced endoscopist in the endoscopy suite.
 
All the procedure will be conducted under deep sedation.
 
SEMS placed will be fully covered.

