**Objectives**

To assess the need for EST before SEMS placement in patients with malignant bile duct obstruction.

To evaluate immediate (periprocedural) and delayed (30 days) post ERCP complications including pancreatitis, SEMS migration, bleeding and perforation.

A sample size analysis to detect superiority at 5% significance level and a power of 80% showed that 500 patients had to be enrolled in each group.

Continuous variables such age will be reported in terms of their mean and range, and t-test will be done to test their main difference.

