**Statistical methods, data analysis**

X square test or Fisher exact test will be carried out for statistical analysis to compare rates of total complications between the two groups and rates of pancreatitis, bleeding, stent migration and perforation.

Wilcoxon Mann-Withney test will be used for comparison of means between 2 continuous variables. A single-tailed P value of less than 0,05 is considered significant.

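### No masking of the patient or of whoever records post-procedure complications is described, so arm-dependent recording can bias the pancreatitis, bleeding and total-complication comparisons

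*Combined protocol and SAP*

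**What the plan says.** Section 1 Summary gives the design as "Prospective randomized, multicenter study. 18 months", and the allocation as "All the patients will be randomly assigned to undergo ERCP with (Group A) or without (Group B) ES before biliary SEMS placement". On who acts and under what conditions it says "All the endoscopic procedures will be performed by experienced endoscopist in the endoscopy suite" and "All the procedure will be conducted under deep sedation".

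The Objectives set the outcomes: "To evaluate immediate (periprocedural) and delayed (30 days) post ERCP complications including pancreatitis, SEMS migration, bleeding and perforation". The section on statistical methods then compares the rate of each of these complications, and of all complications together, by chi-square or Fisher exact test. Its decision rule is "A single-tailed P value of less than 0,05 is considered significant".

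The background says of ES that "EST may facilitate insertion of self expandable metal stent (SEMS) and also help avert the development of pancreatitis from stent-related occlusion of the pancreatic duct". It goes on to link ES itself to pancreatitis, bleeding and perforation. It also cites a guideline that finds ES unnecessary for a single stent, and a later meta-analysis suggesting that ES may lower the pancreatitis rate.

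The available text does not say whether the patient, the ward or follow-up staff, or any adjudicator knows the arm. It gives no criteria for pancreatitis or bleeding and does not say who records them.

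**The concern.** Randomisation makes the arms comparable at the time of the procedure. It does not make the later search for complications comparable. That pancreatitis and delayed bleeding are partly matters of report and judgement is general clinical reasoning, not something the documents state: a patient reports pain, someone decides whether to investigate, and someone decides whether the findings amount to an event. With no written criteria, the plan leaves that judgement open. If those making it know whether ES was done, and hold a view on which complication ES causes or prevents, they can look harder or call an event more readily in one arm.

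This matters because these are the comparisons the trial exists to make, and the total-complication rate inherits any error in its components. A larger sample does not remove such a bias; it only makes the biased difference more precise.

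**Working it through.** **1. Is masking described?** The rows of the Summary on design, intervention, objectives, statistics and timetable were read together. The endoscopist performs or omits ES and so cannot be masked. No masking is stated for anyone else. Sedation applies to both arms, so the patient does not observe the step that distinguishes them; nothing says whether the patient is told afterwards.

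**2. Do staff have arm-specific expectations?**
- Bleeding: the background points one way only, towards more with ES.
- Pancreatitis: it points both ways. ES may avert it by relieving stent-related duct occlusion, yet ES is also listed as a cause.

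**3. The plan's own figure.** The Objectives put the target at 500 per arm, for superiority at the 5% level with 80% power. No event rates, effect size or dropout are given, so 500 cannot be reproduced. It fits more than one assumption: 5% v 9% one-sided needs 503 per group, and 10% v 16% two-sided needs 492. At 500 per group, one-sided 5% and 80% power, the detectable contrasts are about 5% v 9.0% and 10% v 15.2%.

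**4. Illustration of size.** From the plan: n = 500 per group and a one-sided 5% level. Assumed: the two arms have the same true rate; the recorded rate is p₁ = 5% or 10% in one arm and p₂ = 1.2 or 1.3 times that in the other; the single tail lies in the direction of the over-recorded arm. The documents give none of these assumed values.

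With p̄ = (p₁ + p₂)/2, d = p₂ − p₁, SE₀ = √[2p̄(1 − p̄)/n] and SE₁ = √{[p₁(1 − p₁) + p₂(1 − p₂)]/n}, the probability of a significant result is Φ[(d − 1.645·SE₀)/SE₁].

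For p₁ = 5% and ratio 1.2: p̄ = 0.055, and SE₀ = √(2 × 0.055 × 0.945/500) = 0.01442. Then (0.010 − 1.645 × 0.01442)/0.01442 = −0.95, and Φ(−0.95) is about 17%.

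| p₁ | Ratio | p₂ | SE₀ | SE₁ | z | False-positive chance |
|---|---|---|---|---|---|---|
| 5% | 1.2 | 6.0% | 0.01442 | 0.01442 | −0.95 | 17% |
| 5% | 1.3 | 6.5% | 0.01472 | 0.01472 | −0.63 | 27% |
| 10% | 1.2 | 12.0% | 0.01979 | 0.01978 | −0.64 | 26% |
| 10% | 1.3 | 13.0% | 0.02018 | 0.02015 | −0.16 | 44% |

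With equal recording (ratio 1) the formula returns 5%.

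**5. Sensitivity to the test.** The plan does not say whether the chi-square is continuity-corrected. Subtracting 1/n = 0.002 from d gives z = −1.09, −0.76, −0.74 and −0.26, so about 14%, 22%, 23% and 40%. The inflation is smaller but remains.

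**6. In events.** The surplus is 0.010 × 500 = 5 to 0.015 × 500 = 7.5 events at the 5% rate, and 10 to 15 at the 10% rate. In percentage points it is 1.0–1.5 against a detectable 4.0 (9.0 − 5), and 2.0–3.0 against 5.2 (15.2 − 10).

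**The case against.** Several stronger readings are tempting, and the documents do not support them.

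- A reader might infer that the trial is open-label. The text never says so. What is available is a summary, and consent material, where one might expect to find what patients are told, is not part of it. Only the absence of any description can be asserted.
- A reader might infer that the bias would produce more pancreatitis in the arm without ES. The background gives reasons in both directions, so no direction is established for pancreatitis.
- A reader might try to show a definite false positive from a single count. For example, 5% inflated 1.5 times is 37.5 of 500, rounded to 38 against 25. The one-sided P value is 0.045 uncorrected, 0.059 with Yates or Fisher, and 0.051 at the unrounded rates. That result depends on rounding and on the test, so it is not used here.
- A reader might conclude that no observed difference could be told apart from unequal recording. The share of events that rests on judgement is unknown. The argument is made for pancreatitis, delayed bleeding and the total, not for migration or perforation taken singly.
- A reader might call patient masking free because of the sedation. Sedation hides only the procedure; keeping the arm hidden to day 30 takes discipline over notes and conversation.

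One further objection is that looking harder cannot create cases beyond the true number. That is fair, but the calculation uses recorded rates only. The same ratio arises from over-calling in one arm or from under-detection in the other.

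It is also fair that missing outcome criteria are a separate gap. They matter here because they leave room for knowledge of the arm to act. None of these objections supplies the missing masking statement.

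**Conclusion.** The concern stands in a limited form. The available text describes no masking of the patient or of the person recording post-procedure complications, while outcomes without stated criteria are compared to 30 days and staff have arm-specific expectations. Arm-dependent recording can therefore bias the pancreatitis, bleeding and total-complication comparisons. The documents fix neither its direction nor its amount.

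The 17–27% and 26–44% error rates show how little unequal recording is needed; they do not predict what will happen. They rest on the assumed rates, ratios and direction of the tail and on an uncorrected test. The plan does not say which direction its single tail covers. If it is the opposite one, the same unequal recording would lower the chance of a significant result and could hide a real difference.

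This is a worthwhile, low-cost improvement. It is not evidence that the trial's comparison is invalid.

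**What to change.** Add three statements to the protocol, and adapt the data form to match:

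1. The patient is not told the arm until the day-30 contact is complete. Deep sedation in both arms makes this feasible.
2. Post-procedure and day-30 events are collected with one fixed script and a form that does not carry the allocation, by existing staff who were not in the procedure room where such staff are available.
3. Pancreatitis and bleeding are classified by one prespecified rule, applied without knowledge of the arm.

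If any of this is already in place at the sites, saying so in the protocol closes that part of the point. No schedule of tests is proposed, because the documents do not say what is routine.

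The cost is mainly wording and form design, on the assumption that suitable staff exist; the documents do not describe staffing. Limits remain. The endoscopist stays unmasked, so intraprocedural events are still recorded with knowledge of the arm. Sites must also keep the allocation out of ward notes and conversation while preserving access to it in an emergency.

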**Objectives**

To assess the need for EST before SEMS placement in patients with malignant bile duct obstruction.

To evaluate immediate (periprocedural) and delayed (30 days) post ERCP complications including pancreatitis, SEMS migration, bleeding and perforation.

A sample size analysis to detect superiority at 5% significance level and a power of 80% showed that 500 patients had to be enrolled in each group.

Continuous variables such age will be reported in terms of their mean and range, and t-test will be done to test their main difference.

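### Complications are to be judged by a single-tailed P<0.05 with no stated direction and no effect estimate or interval, although the background gives reasons for an effect either way

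*Combined protocol and SAP*

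**What the plan says.** The Objectives section of the combined protocol and SAP opens with "To assess the need for EST before SEMS placement in patients with malignant bile duct obstruction". The sample size statement in the same section reads "A sample size analysis to detect superiority at 5% significance level and a power of 80% showed that 500 patients had to be enrolled" per group. It names no superior arm, event rates or sidedness.

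Under Statistical methods, data analysis, the plan says "X square test or Fisher exact test will be carried out for statistical analysis to compare rates of total complications between the two groups", and extends this to "rates of pancreatitis, bleeding, stent migration and perforation". That makes five comparisons. After a sentence on the Wilcoxon test for continuous variables comes the only threshold in the plan: "A single-tailed P value of less than 0,05 is considered significant". No direction is given for the tail. No risk difference, risk ratio or confidence interval is planned.

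The background in the Summary argues both ways. Sphincterotomy may "help avert the development of pancreatitis from stent-related occlusion of the pancreatic duct", and "a more recent meta analysis showed that ES may decrease the rate of PEP". Against this, "On the other hand, ES is also independently associated with pancreatitis, bleeding, and perforation".

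**The concern.** A single-tailed test is defined by the direction it looks in. Without a stated direction the rule is incomplete, and there are two ways it can go wrong.

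- **Tail fixed, but on the other side from the effect.** A difference in the untested direction is reported as non-significant however large it is. If the tail looks for fewer complications in Group B (no sphincterotomy), no excess in Group B can be declared.
- **Tail chosen after the results are known.** The nominal 5% level no longer holds.

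The background does not settle the direction. For pancreatitis it cites evidence on both sides. For bleeding and perforation it gives reason to expect more events with sphincterotomy. One tail therefore cannot suit all five comparisons.

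The objective adds a further need. Whether sphincterotomy is needed depends on how large an excess of complications without it remains possible. A P-value without an effect estimate and interval does not show that.

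**Working it through.** **Inputs from the documents:** 500 per group, 5% level, 80% power, superiority, single tail with no direction. **Not in the documents:** event rates and the sidedness of the sample size calculation. All counts and rates below are assumptions.

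**1. The plan's own figure.** The 500 per group can be neither reproduced nor refuted. With the usual formula,

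n = [z_α·√(2p̄(1−p̄)) + z_β·√(pA(1−pA)+pB(1−pB))]² / (pA−pB)²,

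both kinds of test fit:

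- One-sided, 5% vs 9%: [1.645×0.3608 + 0.842×0.3597]² / 0.04² = 503 after rounding up.
- Two-sided, 5% vs 9.6%: [1.960×0.3679 + 0.842×0.3664]² / 0.046² = 501 after rounding up.

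**2. What the unstated direction does.** Assume 50/500 events in Group A (10%) and 75/500 in Group B (15%).

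- z = (0.15−0.10)/√(2×0.125×0.875/500) = 0.05/0.02092 = 2.39.
- Tail looking for an excess in B: P = 0.008 (chi-square, uncorrected) or 0.011 (Fisher).
- Tail looking for fewer events in B: P = 0.99 by either test.
- 95% CI for B minus A: 0.05 ± 1.96×√(0.10×0.90/500 + 0.15×0.85/500) = 0.05 ± 1.96×0.02086 = +0.9 to +9.1 points.

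The same data are clearly significant or wholly non-significant, depending on a choice the plan does not record. By symmetry, 75 vs 50 gives the reverse.

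**3. Tail chosen afterwards.** For one comparison under the null, P(z > 1.645) + P(z < −1.645) = 0.05 + 0.05 = 0.10.

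**4. What a non-significant result leaves open.** Even with the tail looking for an excess in B, the largest non-significant Group B counts by one-sided chi-square are:

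| Events A vs B (of 500 each) | One-sided P | 95% CI, B minus A (points) |
|---|---|---|
| 25 vs 37 | 0.058 | −0.6 to +5.4 |
| 50 vs 66 | 0.057 | −0.8 to +7.2 |
| 75 vs 94 | 0.054 | −0.8 to +8.4 |

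With equal observed rates of 5%, 10% and 15%, the half-width 1.96×√(2p(1−p)/500) is 2.7, 3.7 and 4.4 points.

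**5. Effect of two-sided testing on power at 500 per group.** Power = Φ{[d·√500 − z_α·√(2p̄(1−p̄))] / √(pA(1−pA)+pB(1−pB))}, where d is the absolute difference in rates.

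- 5% vs 9%: one-sided Φ[(0.8944−0.5935)/0.3597] = 79.9%; two-sided Φ[(0.8944−0.7072)/0.3597] = 69.9%.
- 9% vs 14%: 79.8% and 69.8%.
- 5% vs 9.6%: two-sided Φ[(1.0286−0.7210)/0.3664] = 79.9%.

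Two-sided testing costs about 10 points of power if 500 was sized one-sided, and nothing against the stated 80% if it was sized two-sided.

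**The case against.** Four objections deserve an answer.

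- **The single-tail sentence follows the Wilcoxon sentence**, so it may not be meant for the complication tests. Applying it to them is an inference, though the likelier one, since the plan gives no other threshold. If it does not apply, the complication tests have no stated criterion at all.
- **The Pearson chi-square statistic has no direction.** Its upper tail picks up differences either way, so the authors may in effect mean a two-sided test. That is possible, but a single-tailed Fisher test does have a direction, and the plan allows either test. If two-sided testing was meant, the proposed text only makes this explicit.
- **A reader can compute an interval from the reported counts.** True, and no data are lost. But the direction of the tail cannot be supplied credibly afterwards, and planning the interval fixes in advance how a null result will be described.
- **This is synopsis-level text**, where omitting an interval is less telling. That tempers the point about the interval. It does not help with the tail, because a single-tailed rule is stated and its direction is not.

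A reader might infer that the investigators mean to take a non-significant result as proof that sphincterotomy is unnecessary. No section says so, and the sample size is described as one for superiority. Failure to bound an excess is common to every superiority test and is not by itself an error.

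**Conclusion.** The concern holds. The plan's only significance criterion is single-tailed without a direction, while its background gives reasons for an effect both ways. If followed, the rule either cannot declare a difference in the untested direction (P = 0.99 where the 95% CI is +0.9 to +9.1 points, in the assumed 50 vs 75 example) or, with a tail picked after the results, tests each comparison at about 10%. The missing effect estimate and interval are a secondary gap, which matters because the objective is about need.

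The conclusion assumes that the single-tail sentence governs the complication tests. The figures also rest on assumed rates, but the logic does not depend on any particular rate.

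Two stronger readings go too far. The documents do not show that 500 per group is wrong, because they give neither rates nor sidedness. Nor do they show that power would fall to 70% under two-sided testing, which is true only if 500 was sized one-sided. The point should be corrected before any outcome comparison; it does not invalidate the design.

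**What to change.** In Statistical methods, data analysis, replace the single-tailed criterion for the complication comparisons with text such as:

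> Total complications and each of the four component complications are compared by chi-square or Fisher exact test, two-sided, with P<0.05 considered significant. For each, the risk difference (Group B minus Group A) is reported with a two-sided 95% CI, using a score or exact method when events are sparse. A non-significant test alone is not reported as showing that sphincterotomy is unnecessary; the CI describes what excess in Group B remains possible.

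In the sample size statement, give the sidedness and the event rates behind 500 per group, and restate the power if it changes.

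Two-sided 5% tests and 95% intervals are at the same level. Keeping a single tail would require a stated direction for each of the five comparisons, would call for a 90% interval to match the test, and would still leave differences in the other direction undeclarable.

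**Cost.** A few lines of text; the intervals use the same event counts as the planned tests.

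- If 500 was sized one-sided, two-sided power is about 70% (assumed 5% vs 9%, or 9% vs 14%). Restoring 80% would take about 638 per group instead of 503, that is 135 more per group. Keeping 500 and stating the lower power is the alternative.
- If 500 was sized two-sided (for example, assumed 5% vs 9.6%), the stated 80% is unchanged.
- A null result may have to be reported as inconclusive.

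### Age is t-tested between randomised groups but left out of the complication comparison, which may forgo a little precision

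*Combined protocol and SAP*

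**What the plan says.** In the Combined protocol and SAP, section 1 Summary gives the allocation: "All the patients will be randomly assigned to undergo ERCP with (Group A) or without (Group B) ES before biliary SEMS placement". The Objectives section covers age: "Continuous variables such age will be reported in terms of their mean and range, and t-test will be done to test their main difference". Age is the only continuous variable named anywhere. Statistical methods, data analysis adds a second test: "Wilcoxon Mann-Withney test will be used for comparison of means between 2 continuous variables". No rule is given for choosing between the two.

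For the outcome, the same section says "X square test or Fisher exact test will be carried out for statistical analysis to compare rates of total complications between the two groups", and applies the same tests to the individual complication types. No regression model, covariate, centre term or stratified analysis is named, although the study is multicentre. The general significance rule is "A single-tailed P value of less than 0,05 is considered significant", with no direction stated.

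**The concern.** Age is settled before a patient is allocated. If allocation is random, any difference in mean age between the groups is due to chance, and the null hypothesis of the t-test is true by design. A significant result is then a false alarm, and a non-significant one gives no assurance. Whether an imbalance matters depends on its size and on how strongly age predicts complications, and the p-value measures neither.

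The one place where a recorded baseline value could help is the treatment comparison, and the plan does not use it there. If age is prognostic, adjusting for it takes chance imbalance out of the treatment contrast and narrows the interval somewhat. If the covariates are not named in advance, a chance difference in age may prompt adjustment after the data have been seen.

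**Working it through.** **Inputs from the documents.** Random assignment (1 Summary). Superiority, 5% significance, 80% power and 500 per group (Objectives). One-sided threshold of 0.05 (Statistical methods, data analysis). No event rates, effect size or covariate strength are given.

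**1. The plan's own figure.** The text reads "A sample size analysis to detect superiority at 5% significance level and a power of 80" per cent, and "500 patients had to be enrolled in each group". Without rates, 500 can be neither reproduced nor refuted. To choose plausible rates, I used

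n per group = [z₁₋α √(2p̄(1−p̄)) + z₀.₈ √(p₁(1−p₁) + p₂(1−p₂))]² / (p₁ − p₂)².

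- One-sided 0.05, 10% vs 5.8%: [1.645 × 0.3815 + 0.842 × 0.3803]² / 0.042² = 509.
- One-sided 0.05, 20% vs 14.1%: 502.
- Two-sided 0.05, 10% vs 5.3%: 501. Two-sided, 20% vs 13.4%: 501.

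The simulations below use 10% vs 5.75% and 20% vs 14.15%. These rates are assumptions that fit 500 per group at one-sided 0.05.

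**2. False alarms from the age test.** One test at 0.05 gives 5%. If a one-sided 0.05 result in either direction counts, the chance is 2 × 0.05 = 10%. In the simulations, a two-sided t-test on the baseline covariate rejected in 3.9% to 5.7% of trials. That is what a true null should give (Monte Carlo standard error √(0.05 × 0.95/3000) = 0.4 points).

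**3. What adjustment could gain.** I simulated 3,000 trials per setting with 500 patients per group and one standard normal baseline covariate. Its odds ratio (OR) per standard deviation (SD) was assumed to be 1.0, 1.5 or 2.0. The unadjusted analysis was the pooled z-test, equivalent to chi-square. The adjusted analysis was a logistic model standardised to a risk difference, RD = (1/N) Σ [p̂(A, xᵢ) − p̂(B, xᵢ)], averaged over all patients.

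| Assumed rates | OR per SD | Power, unadjusted | Power, adjusted | Change (points) | Variance ratio, adjusted/unadjusted |
|---|---|---|---|---|---|
| 10% vs 5.75% | 1.0 | 0.806 | 0.805 | −0.1 | 1.003 |
| 10% vs 5.75% | 1.5 | 0.807 | 0.810 | +0.3 | 0.996 |
| 10% vs 5.75% | 2.0 | 0.806 | 0.813 | +0.8 | 0.957 |
| 20% vs 14.15% | 1.0 | 0.792 | 0.790 | −0.1 | 1.000 |
| 20% vs 14.15% | 1.5 | 0.790 | 0.798 | +0.8 | 0.969 |
| 20% vs 14.15% | 2.0 | 0.787 | 0.812 | +2.5 | 0.948 |

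Changes are taken from the unrounded powers. With equal rates (10% or 20% in both groups), one-sided type I error was 4.3% to 6.0% unadjusted and 4.4% to 5.7% adjusted. Both are close to 5%, so neither analysis is invalid.

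**4. Why centre needs care.** At 10% vs 5.75% the expected number of events is 500 × 0.10 + 500 × 0.0575 = 78.75, about 79. The number of centres is not given. With 30 equal centres (assumption), the mean is 78.75/30 = 2.6 events per centre. The chance that a centre has none is about e^(−2.6) = 0.07, so about 30 × 0.07 = 2 centres would have no events. A separate logistic term for such a centre cannot be estimated.

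**The case against.** The strongest objection is that nothing here is broken. A chi-square or Fisher test of complication rates in a randomised trial is unbiased and holds its type I error, and preferring an adjusted model is partly a matter of taste. The plan also reports mean and range for age, which is proper descriptive practice, and makes no later step depend on the t-test. Dropping that test would change no conclusion of the trial. The wording on continuous variables is not confined to baseline values, and a measure taken after randomisation could properly be tested, though none is named. All of this stands, and it limits the point to a minor one.

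Three stronger readings are tempting, and the documents do not support them:

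- A reader might infer that the lack of adjustment biases the comparison. It does not; at most it costs precision.
- A reader might assume five baseline tests and quote 1 − 0.95⁵ = 22.6% for at least one false alarm, or 1 − 0.90⁵ = 41.0% counting both directions. The arithmetic is right, but only one continuous variable is named, and no rule says that each one-sided test is read both ways.
- A reader might call the precision gain free. The documents do not say that age predicts complications, so the gain can be nil, and a model fitted to few events has its own cost.

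What survives is narrow. The age test tells the reader nothing useful, and pre-specifying adjustment for a value the plan already reports is a cheap change that may help.

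**Conclusion.** This is a minor improvement, not the correction of an error. That the age test is uninformative follows from random assignment and needs no assumed figure. Its false-alarm rate for this one variable is 5%, or 10% if either one-sided direction counts.

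The benefit of adjustment does rest on assumptions: event rates chosen to fit 500 per group, and a covariate odds ratio of 1.0 to 2.0 per SD. Across that range the change in one-sided power is 0 to about 2.5 points. The top of the range appears only at 20% vs 14.15% with an odds ratio of 2.0. At 10% vs 5.75% the largest gain is 0.8 points.

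**What to change.** 1. Report age and any other baseline variables by group without p-values. If a continuous measure taken after randomisation is to be tested, name it and choose one test for it.
2. Pre-specify an overall-complication analysis adjusted for age, for example logistic regression with treatment and age, standardised to a risk difference with its confidence interval. Keep the chi-square or Fisher test as a sensitivity check.
3. If centre is included, use a sparse-data method such as Mantel-Haenszel stratification or pooling of small centres under a rule set in advance. Do not fit one fixed logistic term per centre.
4. Fix the covariate list before outcome data are seen, and keep it short.

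The cost is a few sentences in the analysis plan and slight extra analysis work. No extra patients are needed, and the plan already provides for reporting age. The drawback is some dependence on the model when events are few, which the retained simple test lets a reader check.
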